2.5.3 Handling of missing values/censoring/discontinuations

If a patient has no Week 12 value, the missing value will not be imputed and the patient will be removed from the analysis.

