2.5.4 Supportive analyses

A supportive nonparametric analysis will be performed to examine the consistency of results if the assumption of normality for the distribution of the primary endpoint is not tenable. Graphical methods (e.g., normal probability plot and histogram of residuals) and analytical methods (e.g., Shapiro-Wilk test) will be used to assess the assumption of normality. For this supportive analysis, the primary endpoint will be analyzed using the Wilcoxon rank-sum test. The probability of one treatment being the same or better than the other treatment will be estimated (based on the Wilcoxon rank-sum test) and the associated 95% confidence interval will be reported (Chen and Kianifard, 2000).

The following supportive/sensitivity analyses of the primary endpoint will also be performed:

- An analysis based on the FAS using the same analytical approach as described in Section 2.5.2 where missing values at Week 12 are imputed using the Last Observation Carried Forward (LOCF) procedure (only post-baseline trough values will be carried forward).
- An analysis based on the PPS using the same analytical approach as described in Sections 2.5.2 and 2.5.3.
- Change from baseline in aortic characteristic impedance at Weeks 4 and 12 will be analyzed based on a repeated measures ANCOVA model in which treatment, week, and treatment-by-week interaction will be included as fixed-effect factors and the baseline value as a covariate, with a common unstructured covariance for each treatment group. The primary treatment comparison between sacubitril/valsartan and enalapril will be made at Week 12. The analysis will be performed on all available data in the FAS. The estimated treatment effect with the associated two-sided 95% confidence interval at Week 12 will be provided.
- Subgroup analyses based on the FAS as described in Section 2.2.1.
- An on-treatment analysis based on the FAS using the using the same analytical approach as described in Section 2.5.2.
- Analyses of the “original” and “alternative” aortic characteristic impedance variables based on the FAS using the same analytical approach as described in Section 2.5.2.

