2.14 Interim analysis

No interim analysis is planned.

3 Sample size calculation

In CHOIR (Mitchell 2002), treatment with Omapatrilat was associated with an approximately ~10% reduction in characteristic impedance at 12 weeks, with little or no change seen amongst enalapril- treated patients. Based on a similar study design and population, and accounting for a dropout rate of 20% from first visit to subsequent follow up and a 10% rate of non-evaluable data, assuming a standard deviation of 80 for the primary efficacy variable and 90% power, a sample size of 432 patients (216 per arm) will be necessary to detect a clinically important change of 30 dyne x sec/cm⁵ between the two treatment groups.

Assuming a significance level of 0.05, a sample size 432 patients would provide 88% power to detect a 25% reduction in the geometric mean of the proportional change from baseline to Week 12 in NT-proBNP for the sacubitril and valsartan treatment group assuming a value of 0.95 for the enalapril group, a value of 0.7125 for the sacubitril and valsartan group (25% reduction), a common standard deviation of 0.85 and a 20% drop-out rate. The difference between the logs for the two treatment groups is therefore assumed to be 0.288.

4 Change to protocol specified analyses

The following changes to protocol specified analyses were made:

- Modified baseline definition as follows:
 - Eliminated requirement that assessment date:time is prior to first dose date:time
 - Clarified how baseline assessments for hemodynamic variables will be identified
- Clarified that tables summarizing demographics and baseline data will be run only on the FAS, and not also on the RS as indicated in the protocol
- Indicated that values of the hemodynamic variable carotid-femoral pulse wave velocity will be negative inverse transformed prior to analysis
- Added separate summaries of prior and concomitant CV, HF, ACEi and ARB medications
- Added the following supportive analyses of the primary endpoint:
 - On-treatment analysis

- Analysis using the “original” aortic characteristic impedance variable
- Analysis using the “alternative” aortic characteristic impedance variable
- Added on-treatment analyses of the secondary endpoints
- Modified the PPS definition to clarify that major protocol deviations will exclude patients from the PPS regardless of the study phase in which they occur
- Added summary of the incidence of hypotension through Week 12

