5.5 Statistical models

5.5.1 Primary analysis

The null hypothesis for the primary analysis is the difference between the sacubitril/valsartan and enalapril groups in the mean change from baseline in aortic characteristic impedance at Week 12 is equal to zero. An ANCOVA model will be used. The model will have the change from baseline as the dependent variable with treatment as a fixed effect factor and the baseline value as a covariate. The general form for the ANCOVA model is:

$$y_{ij} = \mu + \alpha_i + \beta(x_{ij} - \bar{x}) + \epsilon_{ij}$$

where i indexes treatment group and j indexes patient within treatment group. PROC MIXED in SAS will be used for the analysis (refer to the SAP TFL shells document for additional details).

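### The supportive repeated-measures model fits one baseline-Zc slope for Weeks 4 and 12, so its Week 12 contrast is not strictly comparable with the primary ANCOVA

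*SAP*

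**What the plan says.** The third supportive analysis in SAP 2.5.4 is specified as follows: "Change from baseline in aortic characteristic impedance at Weeks 4 and 12 will be analyzed based on a repeated measures ANCOVA model". On the fixed effects it says: "treatment, week, and treatment-by-week interaction will be included as fixed-effect factors and the baseline value as a covariate". The covariance is given "with a common unstructured covariance for each treatment group". On the data and the contrast: "The analysis will be performed on all available data in the FAS", and "The primary treatment comparison between sacubitril/valsartan and enalapril will be made at Week 12". No baseline-by-week term appears there or elsewhere in the supplied text.

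The primary model in SAP 5.5.1 is an ANCOVA of the Week 12 change only, adjusted for baseline Zc. Its missing-data rule, in SAP 2.5.3, is complete-case: "If a patient has no Week 12 value, the missing value will not be imputed and the patient will be removed from the analysis". SAP section 3 sizes the trial "accounting for a dropout rate of 20% from first visit to subsequent follow up and a 10% rate of non-evaluable data".

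**The concern.** The interaction with week is written out for treatment but not for baseline. Read literally, one slope of change on baseline Zc serves both weeks, and the Week 4 data help to set the slope used at Week 12.

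There is some reason to expect the slopes to differ. If variances are equal, the slope of change on baseline is the correlation with baseline minus 1, and correlations commonly fall with time. The visits are at Days 28 and 84 (Protocol Table 6-1). The Week 4 trough precedes the step to Dose Level 3, and Week 12 follows about eight weeks at that level (Protocol 5.5.4 and 6.4.1). This is plausibility only: the documents give no slopes or correlations.

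The comparison matters because, among the visible supportive analyses, only this model and LOCF keep a patient who has Week 4 but no Week 12 data. This model is the only likelihood-based check under missing at random. It is most useful if any gap from the primary result can be put down to missing data.

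**Working it through.** **Inputs from the documents.** SD 80, difference 30, 90% power, two-sided 0.05, losses of 20% and 10%, 216 per arm (SAP 2.1 and 3).

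**Inputs assumed.** Baseline slopes, baseline SD, Week 4 to Week 12 correlation, and how missingness relates to baseline and arm. The documents give none of these.

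**The plan's own figure.** 2 × (1.960 + 1.282)² × 80² / 30² = 149.4, so 150 per arm; the t-based value is 151. 151 / (1 − 0.30) = 215.7, so 216 per arm and 432 in total. The stated N reproduces. It concerns the primary analysis; the plan states no figure for the repeated-measures model.

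**Complete data.** Let b12 be the Week 12 slope, b the common slope and Δx the baseline mean difference between arms. The primary estimate is Δy12 − b12·Δx and the supportive one is Δy12 − b·Δx, so

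supportive − primary = (b12 − b) × Δx.

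Randomisation gives Δx mean zero. With an assumed baseline SD of 80 and 151 per arm, its SD is 80 × √(2/151) = 9.2. With true slopes −0.30 and −0.50 the fitted common slope is about −0.42, so the SD of the departure is 0.08 × 9.2 = 0.74. Simulation results:

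| True slopes, Week 4 / Week 12 | SD of departure |
|---|---|
| equal | about 0.25 |
| −0.3 / −0.5 | 0.7 to 0.8 |
| −0.2 / −0.6 | 0.8 to 1.2 |
| Second set, 216 per arm: −0.20 to −0.35 / −0.40 to −0.50 | 0.6 to 1.8 |

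The mean departure was at most 0.1. With a baseline-by-week term the departure was 0.00000 in every setting.

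**Incomplete data.** Let β4 and β12 be the true slopes and γ the regression of the Week 12 residual on the Week 4 residual. Suppose Week 4 is complete and baseline is balanced over all randomised patients. The fit adjusts (y12 − γ·y4) among those seen at Week 12 with slope b(1 − γ), whereas its true slope is β12 − γ·β4. Hence

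bias = [(β12 − b) − γ(β4 − b)] × Δx, with Δx taken among patients seen at Week 12.

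If β4 = β12 = b, the bracket is zero. If missingness depends on baseline in the same way in both arms, Δx is zero. Both conditions are therefore needed. For scale, take slopes −0.30 and −0.50, b = −0.39 and γ = 0.5 (assumed). The bracket is −0.11 − 0.5 × 0.09 = −0.155. A baseline gap of 20, a quarter of an assumed SD of 80, gives 0.155 × 20 = 3.1 in size.

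**Simulated size.** True difference −30, SD of Week 12 change 80, Week 4 complete, 28% missing at Week 12 (1 − 0.8 × 0.9), slopes as in the second set above:

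| Dependence of missingness on baseline (log-odds per SD) | Estimate as written | Size of bias |
|---|---|---|
| none, or the same in both arms | about −30 | none |
| 0.25, one arm | | 0.6 to 1.4 |
| 0.5, one arm | | 1.1 to 2.9 |
| 0.5, opposite by arm | −27.7 to −24.1 | 2.3 to 5.9 |
| 0.5, opposite, signs reversed | −31.6 to −36.6 over two runs | 1.6 to 6.6 |
| 1.0, opposite by arm | −25.7 to −18.0 | 4.3 to 12.0 |
| any of the patterns, equal slopes | within 0.1 of the interaction model | none |

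At 0.5 opposite, the model with baseline-by-week averaged −29.8 to −30.3. A second set, with 18 to 24% dropout and baseline SD 80, gave biases of 1.1 to 5.6 (slopes −0.3/−0.5), 1.3 to 9.8 (−0.2/−0.6) and −2.4 to −13.3 (−0.6/−0.2). The largest values came from strong, opposite dependence. The primary ANCOVA was unbiased throughout.

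**The case against.** The strongest reply is that the model is estimable, prespecified and only supportive. SAP 2.5.2 rests success on the primary ANCOVA alone. The trial is double-blind and double-dummy, and nothing in the documents suggests that missingness would depend on baseline Zc in opposite ways by arm. Protocol 5.6.2 keeps patients who stop drug in the visit schedule, and Table 6-1 asks for the Visit 6 assessments from those who leave during double-blind treatment. Both should limit such missingness. With dependence in one arm at 0.5 per SD, the bias of at most 2.9 is about 0.4 of a standard error near 8. Even at −24.1, with a standard error of about 7.9, z is about 3. All of this stands, and it sets the priority.

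It is also fair that if missingness depends only on baseline and arm, the complete-case primary ANCOVA is already unbiased. The repeated-measures model is most needed when dropout depends on Week 4 response, and these calculations did not examine that case.

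The TFL shells, cited in SAP 5.5.1 for the primary model, might hold code for this model too. They are not among the documents, and the SAP text should settle the point itself.

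What the reply does not answer is that the text lists no baseline-by-week term, so the two analyses of the same contrast adjust for baseline differently.

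**Conclusion.** The specification gap is in the text. Its certain consequence is small: with complete data the supportive Week 12 contrast departs from the primary one with mean zero and SD of about 0.3 to 1.8 dyne·s/cm⁵, against a standard error of 6 to 9. That reduces comparability without biasing the estimate.

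A reader might infer that the model is biased whenever baseline-related dropout differs by arm. The documents do not support that: the true slopes must also differ between Week 4 and Week 12, and the plan gives no data on slopes or on missingness by arm. A reader might also infer that a sound primary result would be made to look weaker. The sign is unknown, and the supportive estimate could equally be inflated.

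Under the assumed slopes and 28% missing, the bias at 0.5 per SD is about 1 to 3 with dependence in one arm and about 2 to 6 with opposite dependence. It grows with stronger dependence and is zero if either condition fails. The primary test, N and alpha are untouched. This is a refinement, not a defect in the trial's main inference.

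**What to change.** In the third supportive analysis of SAP 2.5.4, add a baseline-by-week interaction to the fixed effects, beside treatment, week, treatment-by-week and baseline. With complete data the Week 12 contrast then equals the primary ANCOVA, so a difference between the two reflects how missing data are handled and not a forced slope. In the settings run with equal slopes the extra term cost nothing visible (−30.02 against −30.04). The cost is one model term and one degree of freedom, with no new data. If the TFL shells already contain the term, state it in the SAP text.

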2.1 Data analysis general information

 a Novartis-designated Contract Research Organization (CRO) will be performing all analyses outlined in this SAP. SAS[®] version 9.3 (or higher) will be used for all analyses.

Data from all centers that participate in this protocol will be combined, so that an adequate number of patients will be available for analysis.

Unless otherwise specified, for continuous data, the mean, standard deviation, median, first and third quartiles, interquartile range, and minimum and maximum values will be presented. Geometric means and 95% confidence intervals will also be presented for biomarker data. For categorical data, frequencies and percentages will be presented. All statistical tests will be conducted against a two-sided alternative hypothesis, employing a significance level of 0.05.

All data will be provided in listings in addition to summaries described below.

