2.2.1 Subgroup of interest

The following subgroups will be analyzed for the primary objective:

1. Age groups (<65, ≥65 years; and <75, ≥75 years)
2. Baseline ejection fraction categories based on echocardiography (<25%, 25% - <35%, ≥35%)
3. Prior ACEi/ARB exposure groups (never exposed, previously exposed, or currently taking)
4. Prior ACEi/ARB dose groups (low dose, high dose) (e.g., low dose: <10 mg enalapril daily [or equivalent]; high dose: ≥10 mg enalapril daily [or equivalent])

5. Baseline quartiles of aortic characteristic impedance (based on FAS)
6. Baseline estimated glomerular filtration rate (eGFR) categories (<45, 45 - <60, ≥60 ml/min/1.73 m²)
7. Groups defined by quintiles of change from baseline in mean arterial pressure at Week 12 (based on FAS)
8. New York Heart Association (NYHA) classification [best value during the past month prior to screening visit] (I, II, III, IV)
9. Prior heart failure hospitalization (No, Yes)
10. Prior diabetes (No, Yes)
11. Baseline plasma NT-proBNP (pg/mL) categories (≤ median, > median) (based on FAS)

See Section 2.5 for further details on the primary objective.

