2.5.2 Statistical hypothesis, model, and method of analysis

Let μ_j denote the population mean of change from baseline in the aortic characteristic impedance at Week 12 for treatment group j , $j = 0, 1$, where 0 corresponds to enalapril and 1 corresponds to sacubitril/valsartan.

The following null hypothesis (H_0) will be tested against the alternative hypothesis (H_A):

$$H_0: \mu_1 - \mu_0 = 0$$

$$H_A: \mu_1 - \mu_0 \neq 0$$

The primary endpoint will be analyzed by an analysis of covariance (ANCOVA) model with treatment and Z_c baseline as explanatory variables (Mitchell 2002). The least squares means of the two treatment groups, least squares mean difference of the treatment groups, 95% confidence interval for the difference in the two treatment groups, and p-value based on the fitted linear model will be reported. If the p-value is < 0.05 and the least squares mean difference

of the treatment groups favors sacubitril/valsartan, statistical significance in favor of sacubitril/valsartan is shown.

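### The SAP lists 12 subgroup factors (34 levels) for the primary endpoint but states no subgroup model and no treatment-by-subgroup interaction test

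*SAP*

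**What the plan says.** SAP 2.2.1 opens its list with "The following subgroups will be analyzed for the primary objective" and then gives 11 numbered items. Item 1 holds two age splits, so there are 12 factors. Their levels are: age 2 + 2, ejection fraction 3, prior ACEi/ARB exposure 3, prior ACEi/ARB dose 2, baseline Zc 4, eGFR 3, mean arterial pressure (MAP) change 5, NYHA class 4, prior heart failure hospitalization 2, diabetes 2, NT-proBNP 2. The sum is 34. Item 7 is not a baseline factor: "Groups defined by quintiles of change from baseline in mean arterial pressure at Week 12 (based on FAS".

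SAP 2.2.1 sends the reader to Section 2.5 for detail. There, 2.5.4 has only the bullet "Subgroup analyses based on the FAS as described in Section 2.2.1". The bullets around it for LOCF, the per-protocol set, the on-treatment analysis and the other Zc variables each refer to the approach of 2.5.2; the subgroup bullet does not.

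The primary model is given in 2.5.2: "The primary endpoint will be analyzed by an analysis of covariance (ANCOVA) model with treatment and Z_c baseline as explanatory variables". SAP 5.5.1 repeats it as an equation with the same two terms. The only interaction in the readable SAP belongs to the repeated measures model, in which "treatment, week, and treatment-by-week interaction will be included as fixed-effect factors and the baseline value as a covariate".

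SAP 2.1 adds the general rule "All statistical tests will be conducted against a two-sided alternative hypothesis, employing a significance level of 0.05". Protocol 9.4.4 mentions no subgroup analysis, so the SAP is where the method has to be stated.

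**The concern.** A subgroup analysis of a primary endpoint is read to learn whether the treatment effect differs between kinds of patient. That needs a direct comparison of the effects, normally a treatment-by-subgroup term. The plan commits to 34 levels without saying how they will be analysed. If the 2.5.2 model is fitted level by level, the output is a set of effects and p-values, none of which tests a difference between levels.

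Several factors invite statements about who responds: NYHA class (Protocol 3.6.2 stresses that class I patients had not been treated with this drug in a trial before), prior ACEi/ARB exposure, NT-proBNP and baseline Zc. Levels hold a half to a quarter of the patients, so uneven significance across levels is the expected result even if the effect is the same everywhere. With no stated model, the method could also be chosen after unblinding.

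**Working it through.** **Inputs.** SAP Section 3 (Sample size calculation): "assuming a standard deviation of 80 for the primary efficacy variable and 90% power"; a "clinically important change of 30 dyne x sec/cm"⁵; 20% dropout and 10% non-evaluable data; 432 patients, 216 per arm. Alpha is two-sided 0.05 (SAP 2.1).

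**Reproducing the plan's figure.** Normal formula: n = 2 × (1.960 + 1.282)² × (80/30)² = 149.4, so 150 per arm. The t-based n is 150.4, so 151 per arm. With 30% total loss, 151/0.70 = 215.7, giving 216 per arm and 432 in total. The stated size is reproduced. Compounding the losses (0.8 × 0.9 = 0.72) would give only 418. I therefore take 432 × 0.70 = 302 evaluable, 151 per arm.

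**Power within a level, identical true effect of 30.** Assume a factor has L equal-sized levels, so n per arm per level is 151/L and the standard error is 80 × √(2/n). Let p be the two-sample t power. The chance that some but not all levels reach p < 0.05 is 1 − p^L − (1 − p)^L.

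| Levels | n per arm | SE | Power p | Mixed pattern |
|---|---|---|---|---|
| 2 | 75.5 | 13.0 | 0.629 | 1 − 0.629² − 0.371² = 0.47 |
| 3 | 50.3 | 15.9 | 0.461 | 1 − 0.461³ − 0.539³ = 0.75 |
| 4 | 37.75 | 18.4 | 0.363 | 1 − 0.363⁴ − 0.637⁴ = 0.82 |

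*Sensitivity to the loss assumption.* At 216 × 0.72 = 155.5 per arm (normal approximation), power is 65%, 48% and 38%, and the mixed-pattern chance 46%, 75% and 83%. The choice hardly matters.

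**Across factors.** Leave out the MAP-change quintiles and count NYHA as three levels, since class IV is not eligible. The 11 baseline factors are then six with two levels, four with three and one with four. The expected number with a mixed pattern is 6 × 0.467 + 4 × 0.746 + 1 × 0.818 = 6.6 of 11, with no effect modification at all. One interaction test per factor would be expected to flag 11 × 0.05 = 0.55.

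**What an interaction test can and cannot do.** For a factor split in half, the standard error of the difference between the two effects is 80 × √(2/75.5) × √2 = 18.4. Power for a 30-unit difference is Φ(30/18.4 − 1.96) = Φ(−0.33) = 37%, or 38% at 155.5 per arm. The difference detectable with 80% power is 2.80 × 18.4 ≈ 52. With no effect modification, the chance of at least one p < 0.05 is 1 − 0.95¹¹ = 43% for 11 independent tests and 1 − 0.95¹² = 46% for 12.

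**The case against.** The strongest reply is that the plan is silent rather than wrong. A reader might infer that it schedules 34 separate within-level tests at 0.05. The documents do not say so: the subgroup bullet gives no model and, unlike its neighbours, does not point to 2.5.2. The 0.05 rule in SAP 2.1 fixes alpha and sidedness for whatever tests are run; it does not show that any within-level test is planned. Level-wise estimates with confidence intervals would equally satisfy the text. This stands. Within-level fitting is only the natural default.

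A reader might also infer that chance differences will be reported as effect modification. That does not follow. It needs someone to compare significance between levels, no section sets such a rule, and the analyses sit under supportive/sensitivity analyses. The only success rule, in 2.5.2, concerns the overall comparison.

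The figures are conditional. Nothing in the documents supports equal thirds for ejection fraction, eGFR, NYHA class or ACEi/ARB exposure. The two age splits overlap, and prior dose can be defined only in exposed patients, so the factors are not independent. Interaction tests also bring their own false positives and low power, so they have to come with a stated caveat.

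Finally, SAP 5.5.1 refers to a TFL shells document that was not available, and parts of both documents are redacted. A method could be stated there. However, SAP 2.2.1 and 2.5, where it belongs, show no redaction.

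**Conclusion.** The concern holds as an omission. For 12 factors and 34 levels, the readable SAP gives no subgroup model, no treatment-by-subgroup test and no rule for reading the results. Applied level by level, the one available ANCOVA cannot tell whether the effect differs between levels. If significance were compared anyway, a uniform effect of 30 would give a mixed pattern with a chance of about 47% in a two-level factor, 75% in a three-level factor and 82% in quartiles. These figures rest on about 302 evaluable patients, equal-sized levels and SD 80.

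The primary conclusion of the trial is not affected. What is affected is whether anything can validly be said about effect modification. The gap is worth closing because it costs almost nothing.

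**What to change.** In SAP 2.5.4, replace the subgroup bullet with a specified analysis:

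- For each baseline factor, fit one ANCOVA on the FAS: Zc change on treatment, baseline Zc, subgroup and treatment-by-subgroup. Report the interaction p-value and the treatment difference with 95% confidence interval in each level, without within-level p-values.
- For baseline Zc, test the continuous treatment-by-baseline interaction and keep the quartiles for display.
- State that these analyses are exploratory, unadjusted for multiplicity (about a 43–46% chance of at least one false-positive interaction over 11–12 independent tests) and low-powered (about 37–38% for a 30-unit difference between halves), so a non-significant interaction does not show equal effects.
- Take the MAP-change quintiles out of the subgroup list, or present them separately as a descriptive post-randomization grouping. Treatment can affect which quintile a patient falls in, so an interaction test does not make this a baseline subgroup.

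The cost is SAP wording and programming. No new data are needed, and the primary analysis is unchanged. If the TFL shells already contain such a model, move it into the SAP text.
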